Appendix F
Guidelines for Determination of Laxative Response Status

1. GUIDELINES FOR DETERMINATION OF LAXATIVE RESPONSE STATUS

At the Screening visit, each patient's laxative response status will be determined based on 4 questions which explore the frequency of laxative use, constipation symptom severity, and laxative side-effects during the previous 2 weeks. The patients will be classified as LIR, LAR, or LUR based on their answers. Patients who report having used laxatives over the previous 2 weeks will be asked about the frequency of laxative use (total days used) and constipation symptom severity.

- If the patient reports having used laxative(s) on a minimum of 4 days with continued moderate, severe, or very severe stool symptoms in response to at least 1 of the symptom questions, he/she will be classified as LIR. In addition, patients who report side-effects from laxatives will be classified as LIR.
- If the patient reports having used laxative(s) on a minimum of 4 days and reports absent or minimal constipation symptoms (as defined above) over the previous 2 weeks and no associated side-effects from laxatives, he/she will be classified as LAR.
- If the patient reports no use of laxatives over the previous 2 weeks, or reports infrequent use, as defined by less than 4 daily laxative uses over the previous 2 weeks, he/she will be classified as LUR.

Figure 1 Determination of Laxative Response Status

Clinical Study Protocol Appendix G

Drug Substance	NKTR-118
Study Code	D3820C00008
Edition Number	1.0
Date	[REDACTED]

Appendix G
Child-Pugh Classification

1. CRITERIA FOR CHILD-PUGH CLASSIFICATION

Table 1 Criteria for Child-Pugh Classification

	Points Scored for Observed Findings		
	1	2	3
Encephalopathy grade*	none	1 or 2	3 or 4
Ascites	absent	slight	moderate
Serum bilirubin, mg/dL	<2	2 to 3	>3
Serum albumin, g/dL	>3.5	2.8 to 3.5	<2.8
Prothrombin time, sec prolonged	<4	4 to 6	>6

*Grade 0: normal consciousness, personality, neurological examination
Grade 1: restless, sleep disturbed, irritable/agitated, tremor, impaired handwriting
Grade 2: lethargic, time-disoriented, inappropriate, asterixis, ataxia
Grade 3: somnolent, stuporous, place-disoriented, hyperactive reflexes, rigidity
Grade 4: unrousable coma, no personality/behavior, decerebrate

Mild=5 or 6 points; Moderate=7 to 9 points; Severe =10 to 15 points

Appendix H
Morphine Equivalents Conversion Chart

1. MORPHINE EQUIVALENTS CONVERSION CHART

Table 1 Dose Equivalents for Opioid Analgesics

Oral Dose (mg)	Analgesic	Parenteral Dose (mg)	Oral Morphine Equivalents (mg)
15	Morphine	5	15
100	Codeine	60	15
-	Fentanyl ^a	0.1 (intravenous)	15
10	Hydrocodone	-	15
4	Hydromorphone	1.5	15
2	Levorphanol	1	15
150	Meperidine	50	15
5	Methadone	5	15
10	Oxycodone	-	15
5	Oxymorphone	1	15
100	Propoxyphene	-	15
60	Tapentadol	-	15
67.5	Tramadol	-	15

Note: All doses listed in the above chart will be regarded as equianalgesic. For example, 10 mg of oral hydrocodone corresponds to 15 mg of oral morphine equivalents. And one mg of parenteral oxymorphone is considered to be equivalent to 15 mg of oral morphine.

^a For the 72 hr fentanyl patch (25 µg/hr), the equianalgesic daily dose of oral morphine will be considered to be 15 mg every 4 hh OR 45 mg BID of MS-Contin (i.e., 90 mg/day of morphine). For transmucosal fentanyl (i.e., the fentanyl “lollipop”), an 800 µg dose will be regarded as equivalent to 30 mg of oral morphine.

Clinical Study Protocol Appendix I

Drug Substance	NKTR-118
Study Code	D3820C00008
Edition Number	1.0
Date	██████████

Appendix I
Highly Effective Forms of Birth Control

1. HIGHLY EFFECTIVE FORMS OF BIRTH CONTROL

1. Total sexual abstinence (for the total duration of the trial including the followup period)
2. Vasectomized sexual partner (with participant assurance that partner received post-vasectomy confirmation of azoospermia)
3. Tubal occlusion
4. Intra-uterine Device (provided that coils are copper-banded)
5. Levonorgestrel Intrauterine System (e.g. Mirena)
6. Medroxyprogesterone injections (Depo-Provera)
7. Etonogestrel implants (Implanon, Norplan)
8. Normal and low dose combined oral pills
9. Norelgestromin / ethinylestradiol transdermal system
10. Intravaginal device (e.g., ethinylestradiol and etonogestrel)
11. Cerazette (desogestrel)

In addition to the use of a highly effective form of birth control, WOCBP are instructed to use a barrier method of contraception during sexual intercourse (female or male condom).

The following methods are considered **NOT** to be highly effective and are therefore not acceptable contraceptive methods in NKTR-118 trials

1. Triphasic combined oral contraceptives
2. All progesterone only pills, except Cerazette
3. All barrier methods, if intended to be used alone
4. Non-copper containing IUDs
5. Fertility awareness methods
6. Coitus interruptus

Clinical Study Protocol Appendix J

Drug Substance	NKTR-118
Study Code	D3820C00008
Edition Number	1.0
Date	██████████

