Adult patients who are receiving a stable maintenance opioid regimen (total daily dose of 30 to 1000 mg of oral morphine, or equianalgesic amount[s] of 1 or more other opioid therapies for a minimum of 4 weeks) for non-cancer-related pain and who report a history of <3 spontaneous bowel movements (SBMs)/week and at least 1 OIC associated symptom at screening and have a confirmed diagnosis of OIC will be eligible to be randomized.

Confirmed OIC is defined as:

- Documented <3 SBMs/week on average over the 2-week OIC confirmation period. Patients with uneven distribution of SBMs across the 2-week OIC confirmation period (0 SBMs in 1 week with ≥ 4 SBMs in the other week) will be excluded. In

addition to the SBM frequency criterion, patients must report ≥ 1 of the following symptoms in at least 25% of the bowel movements (BMs) recorded in the electronic diary (eDiary) during the OIC confirmation period: Bristol Stool Scale (BSS) stool type 1 or 2; moderate, severe or very severe straining, incomplete BM. Patients who have 0 BMs over the 2-week OIC confirmation period will not be randomized.

Investigational product, dosage and mode of administration

NKTR-118 25 mg tablets

Comparator, dosage and mode of administration

The study will include a Usual Care arm. For the Usual Care arm, investigators will be permitted to choose constipation treatment according to their best clinical judgment.

Duration of treatment

The study duration will be 54 to 58 weeks. The study will consist of 52 weeks of open-label treatment followed by a 2 week follow-up period. In addition, new patients will undergo an initial screening period lasting up to 2 weeks, and a 2-week OIC confirmation period, during which the diagnosis of OIC and stability of opioid regimen will be confirmed.

Outcome variable(s):

- **Safety**
 - Incidence, nature, and intensity of adverse events (AEs), treatment-related AEs, serious adverse events (SAEs), AEs leading to discontinuation, and specific safety areas of interest
 - Mean daily prescribed opioid dose
 - Mean bisacodyl dose per week (NKTR-118 group only)
 - Change from baseline in Numeric Rating Scale (NRS) pain score
 - Observed values and change from baseline in composite score of modified Himmelsbach scale
 - Changes in vital signs and physical examination
 - Changes in laboratory assessments (ie, chemistry, hematology, and urinalysis [U/A])
 - Changes in electrocardiograms (ECGs)
- **Health economics**

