3.1 Overall study design and flow chart

This is a Phase III, 52-week, multi-center, open-label, randomized, parallel group, safety and tolerability study of NKTR-118 in the treatment of OIC in patients with non-cancer-related pain. This will be a study with global participation that may include the following countries: Australia, Belgium, Canada, Croatia, the Czech Republic, France, Germany, Hungary, Israel, Slovakia, Spain, the United Kingdom (UK), and the United States (US). Eligible patients will be randomized in a 2:1 ratio to receive either NKTR-118 25 mg daily (QD) or Usual Care treatment for OIC (see Section 5.5.2.2). Patients entering the study may enroll directly from 12-week pivotal study D3820C00005, directly from the 3-month safety extension (Study D3820C00007) of the 12-week pivotal study D3820C00004, or may be “new patients” who have not previously participated in a NKTR-118 study. Approximately 1135 patients will be randomized, to obtain approximately 125 patients treated with NKTR-118 for 12 months at approximately 130 centers. The number of patients randomized may be adjusted during the study in order to achieve approximately 125 patients with at least 12 months of exposure to NKTR-118. The study will continue until all enrolled patients have completed.

The study duration will be 54 to 58 weeks. New patients will undergo an initial screening period lasting up to 2 weeks, a 2-week OIC confirmation period (during which the diagnosis of OIC and stability of opioid regimen will be confirmed), and a 52-week treatment period, followed by a 2 week follow-up period. Patients enrolling from another study (also referred to as ‘rollover patients’) will do so on the last day of the treatment period of the previous study, at which time they will start the 52-week treatment period, followed by the follow-up visit 2 weeks after the last dose of study drug. Study assessments during the 52-week treatment and follow-up period will be the same for all patients (new patients as well as patients who previously participated in NKTR-118 studies D3820C00005 or D3820C00007).

New Patients

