3.1.3 Final Visit (Visit R16, 2 weeks after Month 12)

Visit R16 will occur 2 weeks after Month 12 and will also have a ± 3 day allowable scheduling window. At Visit R16, the following procedures will be performed:

- OIC Healthcare Resource Utilization questionnaire will be completed.
- Sitting blood pressure and pulse must be measured. Please see Section 6.3.12.1 for additional details on the protocol-mandated methods for collection of vital signs. The accurate time in date, hours and minutes will be recorded for this measurement.
- Single 12-lead ECG will be collected.
- Blood samples will be collected for laboratory assessments (clinical chemistry and hematology).
- Serum pregnancy test (WOCBP) will be collected.
- C-SSRS to assess suicidal risk, ideation, and behavior

- Daily maintenance and breakthrough pain opioid dosing regimens will be asked about and recorded on the appropriate eCRFs.
- Laxative medication will be asked about and recorded on the laxative medication eCRF. (For NKTR-118 patients, bisacodyl use will be captured on the bisacodyl drug accountability eCRF).
- Use of concomitant medication (other than laxative medication or opioid medication) since previous visit will be recorded.
- AEs since the previous visit will be recorded.

Table 1 Study Plan

Week/month	New Patients		All Patients															
	Screening	OIC Conf	Treatment Period															Final
	-W4 to -W2 ^a	-W2 to W0	W0	W1	W2	M1	M2	M3	M4	M5	M6	M7	M8	M9	M10	M11	M12 ^c	+2W
Visits	S1	S2	R1 ^b	R2	R3	R4	R5	R6	R7	R8	R9	R10	R11	R12	R13	R14	R15	R16
Visit Window (Days)			+3		±3	±3	±3	±3	±3	±3	±3	±3	±3	±3	±3	±3	±3	±3
Informed consent (& genetic informed consent) ^d	√		√ ^e															
Inclusion/Exclusion criteria	√		√															
Randomization			√															
Demographic information	√		√ ^e															
Medical and surgical history (including OIC history)	√		√ ^e															
CRC risk factor evaluation (including FIT as necessary)	√																	
Complete physical examination (height, weight, temperature, respiratory rate) including rectal examination ^f	√		√ ^{e, f}								√						√	
Sitting blood pressure, pulse ^v	√		√	√	√	√		√			√			√			√	√
LIR, LAR, LUR status ^g	√		√ ^e															

Table 1 Study Plan

Week/month	New Patients		All Patients															
	Screening	OIC Conf	Treatment Period															Final
	-W4 to -W2 ^a	-W2 to W0	W0	W1	W2	M1	M2	M3	M4	M5	M6	M7	M8	M9	M10	M11	M12 ^c	+2W

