6. NEW PATIENTS ONLY: Patients must comply with CRC screening criteria as specified in [Appendix E](#).
7. Male patients who are sexually active must use a double-barrier method of contraception (condom with spermicide) from the first dose of investigational product (IP) until 12 weeks after their last dose. Women of childbearing potential must have a negative pregnancy test and confirmed (by the investigator) use of a highly effective form of birth control for 12 weeks before enrollment and until 12 weeks after their last dose. Highly effective forms of birth control are listed in [Appendix I](#). Women of non-childbearing potential can participate in this study without adherence to the pregnancy precautions. Women of non-childbearing potential are defined as women who are either permanently sterilized (hysterectomy or bilateral oophorectomy or bilateral salpingectomy) or are postmenopausal. Any woman who is older than 57 years of age is considered postmenopausal. In addition, women who are older than 50 years of age and amenorrheic with at least 12 months having passed since the last menses (after cessation of all exogenous hormone treatments), are also considered postmenopausal.
8. Be able to understand and comply with the requirements of the study, as judged by the investigator (includes ability to read and write and use the eDiary device)
9. Outpatient status at enrollment and randomization.

In addition, for inclusion in the genetic research, patients must fulfill the inclusion criterion outlined in [Appendix D](#) of this CSP.

If a patient declines to participate in the genetic research, there will be no penalty or loss of benefit to the patient. The patient will not be excluded from other aspects of the study described in this CSP, so long as they consent.

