13.3 Pregnancy

All outcomes of pregnancy should be reported to AstraZeneca or its representative on the pregnancy form. The outcomes of any conception occurring from the date of the first dose until 12 weeks after the date of last dose must be followed up and documented.

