13.3.1 Maternal exposure

Requirements for contraception in WOCBP are specified in Inclusion Criterion #7 (see Section 4.1).

If a patient becomes pregnant during the course of the study, IP should be discontinued immediately.

In clinical studies, when a study participant becomes pregnant, the PREGREP module is used to report the pregnancy, and the PREGOUT module is used to record the outcome.

Pregnancy itself is not regarded as an AE unless there is a suspicion that the IP under study may have interfered with the effectiveness of a contraceptive medication. Congenital abnormalities/birth defects, spontaneous miscarriages or ectopic pregnancy should be reported and handled as SAEs. Elective abortions without complications should not be handled as AEs. The outcome of all pregnancies (spontaneous miscarriage, elective termination, ectopic pregnancy, normal birth, or congenital abnormality) should be followed up and documented even if the patient was discontinued from the study.

If any pregnancy occurs in the course of the study, then investigators or other site personnel must inform appropriate AstraZeneca representatives **within 1 day**, ie, immediately, but no later than the **end of the next business day** of when he or she becomes aware of it.

The designated AstraZeneca representative works with the investigator to ensure that all relevant information is provided to the AstraZeneca Patient Safety data entry site within 1 or 5 days for SAEs, see Section 6.3.5 and within 30 days for all other pregnancies.

The same timelines apply when outcome information is available.

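### Appendix I lets abstinence as contraception end about 10 weeks earlier than inclusion criterion 7 requires

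*Protocol*

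**What the plan says.** Protocol Section 4.1, criterion 7, requires of women of childbearing potential the confirmed "use of a highly effective form of birth control for 12 weeks before enrollment and until 12 weeks after their last dose". For the methods that qualify it refers the reader on: "Highly effective forms of birth control are listed in" Appendix I. Section 13.3.1 confirms which text sets the rule: "Requirements for contraception in WOCBP are specified in Inclusion Criterion #7".

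Appendix I lists 11 methods as highly effective. Item 1 reads "Total sexual abstinence (for the total duration of the trial including the followup period"; the parenthesis closes there. None of the other ten items states a period.

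The length of follow-up is given in three places:

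- Synopsis, duration of treatment: "The study will consist of 52 weeks of open-label treatment followed by a 2 week follow-up period".
- Section 3.1, for rollover patients: "followed by the follow-up visit 2 weeks after the last dose of study drug".
- Section 3.1.3: "Visit R16 will occur 2 weeks after Month 12".

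Section 13.3 applies the same 12-week post-dose window to pregnancy reporting: "The outcomes of any conception occurring from the date of the first dose until 12 weeks after the date of last dose" are to be followed up and documented.

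**The concern.** The protocol states two periods for one duty. Methods 2 to 11 take their period from criterion 7. Abstinence alone carries its own, and that period stops at the end of a 2-week follow-up.

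Appendix I is the list a site is sent to when it discusses methods with a patient. Read literally, item 1 lets a woman relying on abstinence regard her obligation as finished at Visit R16. The sponsor uses the 12-week window consistently elsewhere: in criterion 7 for both sexes, in Section 13.3 for conceptions and in Section 13.3.2 for male patients. The last scheduled pregnancy test is also at R16, so the weeks after it depend on the contraception instruction being right. Item 1 also leaves out the 12 weeks before enrollment that criterion 7 requires.

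**Working it through.** The check is calendar arithmetic.

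**Inputs**

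- Treatment period: 52 weeks (Synopsis; Section 3.1).
- Follow-up period: 2 weeks (Synopsis; Sections 3.1 and 3.1.3).
- Screening and OIC confirmation for new patients: up to 2 weeks plus 2 weeks (Section 3.1).
- Contraception required after last dose: 12 weeks (Section 4.1, criterion 7).

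**Step 1: reproduce the protocol's own duration.** Sections 3.1 and the Synopsis state 54 to 58 weeks per patient.

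- Rollover patient: 52 + 2 = 54 weeks.
- New patient, maximum: 2 + 2 + 52 + 2 = 58 weeks.

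Both ends are reproduced, so the trial including its follow-up period contains 2 weeks after the end of treatment.

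**Step 2: compare the two end points for an on-schedule completer.**

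| Text | End, weeks after randomization | Days after last dose |
|---|---|---|
| Appendix I item 1 | 52 + 2 = 54 | 2 × 7 = 14 |
| Criterion 7 | 52 + 12 = 64 | 12 × 7 = 84 |
| Difference | 10 weeks | 84 − 14 = 70 days |

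**Step 3: visit windows.** R15 and R16 each have a window of ±3 days. Assume the last dose is taken on the day of R15 and both windows are counted from the nominal schedule. Follow-up then ends between 14 − 3 − 3 = 8 and 14 + 3 + 3 = 20 days after last dose, and the gap lies between 84 − 20 = 64 and 84 − 8 = 76 days. No combination of windows closes it. The range is a sensitivity check under that assumption; the protocol does not state it.

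**Step 4: other readings of item 1.**

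- *The follow-up period means the 12-week pregnancy window.* The protocol calls only the 2-week period the follow-up period. Section 13.3 requires conceptions to be tracked for 12 weeks but does not use that term for them.
- *The trial already contains the 12 weeks.* A 52 + 12 = 64-week span does not fit within 54 to 58 weeks. Section 13.3.2, written for male patients, also counts the 12 weeks in addition to the study.
- *The trial means the whole study, to the last visit of the last patient (Section 9.5).* Each woman would have a different end date, unknown in advance, and it would still not be the criterion 7 period.

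**Not computed.** The 10-week figure does not apply to early discontinuers. Under Section 5.8 they have an early termination visit, with a further visit 1 week after discontinuation only if safety results are clinically significant or abnormal.

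**The case against.** The strongest reply is that the texts are compatible: criterion 7 says when contraception is needed, and Appendix I says only which methods count. Other parentheses in the list are qualifying conditions, such as confirmed azoospermia in a vasectomized partner or copper-banded coils. Item 1 can be read the same way, as requiring abstinence to be total and sustained. A woman who abstains for the whole criterion 7 period satisfies both texts, and nothing in Appendix I releases her from the 12 weeks. Harm requires a site to take a duration from a methods list and overlook the criterion that refers to it. What women are told also depends on the consent form, which is not available for review. Finally, Usual Care patients receive no NKTR-118, so concern about conception after exposure in this study is confined to the NKTR-118 arm.

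Much of this stands. Criterion 7 does govern, the risk runs through misreading, and the women affected are a subset whose size is unknown. The Section 13.3.2 comparison is supporting evidence only, because it concerns men. The missing 12 weeks before enrollment add little, since criterion 7 states them itself.

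The reply does not remove the problem. Knowing which text prevails does not take a shorter stated period out of the list that sites are told to consult. The other qualifiers cited describe the method or device; this one states a time span, and the span is too short.

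**Conclusion.** The inconsistency is real. For a woman of childbearing potential who relies on abstinence and completes on schedule, Appendix I item 1 ends about 2 weeks after last dose and criterion 7 ends 12 weeks after, a shortfall of about 10 weeks. This rests on the 2-week follow-up period named in the Synopsis and Sections 3.1 and 3.1.3, and on the last dose falling at the end of Week 52. It affects one of 11 methods and an unstated number of women. The formal duty in criterion 7 is unaffected, and so are the analysis, sample size and enrolment. It is a minor point, worth correcting because the wording is a participant-safety instruction.

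**What to change.** In Appendix I item 1, replace the parenthesis with: *for the full period required by Inclusion Criterion 7, ie, from 12 weeks before enrollment until 12 weeks after the last dose*. A bare cross-reference to criterion 7 would also serve and would leave the period stated in one place only. The change adds no duty, because criterion 7 already imposes the full period. The cost is one parenthesis in one appendix, with no consequence for analysis, sample size or enrolment.

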Appendix J
Drugs that prolong QT/QTc interval

1. DRUGS THAT PROLONG QT/QTC INTERVAL

This list should not be considered comprehensive therefore investigators need to use their judgment when reviewing the medication list from individual patients and restrict patients who must stay on drugs that may increase the QT interval.

Table 1 **Drugs that Prolong QT/QTc Interval**

Concomitant Medication	Class
Disopyramide	Antiarrhythmic 1A
Procainamide	Antiarrhythmic 1A
Quinidine	Antiarrhythmic 1A
Mexiletine	Antiarrhythmic 1B
Propafenone	Antiarrhythmic 1C
Flecainide	Antiarrhythmic 1C
Amiodarone	Antiarrhythmic III
Dofetilide	Antiarrhythmic III
Ibutilide	Antiarrhythmic III
Sotalol	β blocking agent III
Bepriidil	Ca channel blocker IV
Metoclopramide	Prokinetic
Dolasetron	Anti-emetic
Granisetron	Anti-emetic
Ondansetron	Anti-emetic
Droperidol	Anti-emetic
Levomethadyl	Opioid agonist
Methadone	Opioid agonist
Chlorpromazine	Antipsychotic
Haloperidol	Antipsychotic
Pimozide	Antipsychotic
Thioridazine	Antipsychotic
Risperidone	Antipsychotic
Ziprasidone	Antipsychotic
Amitriptyline	Antidepressant
Nortriptyline	Antidepressant
Protriptyline	Antidepressant
Desipramine	Antidepressant

Clinical Study Protocol Appendix K

Drug Substance	NKTR-118
Study Code	D3820C00008
Edition Number	1.0
Date	[REDACTED]

